## 1. Purpose/Specific Aims

This project will evaluate the expression of a receptor called podoplanin (PDPN) in cells from oral cancers and precancerous lesions. We will also determine how sensitive oral cancer cells are to a potential drug called Maackia amurensis seed lectin (MASL).

### 1.1 Objectives

Oral cancers will be biopsied by [name], [name], [name] and [name] and [name]. Precancerous oral lesions will be biopsied by [name]. For oral cancer/precancer patients biopsied at an outside institution and referred to Rutgers/University Hospital for care, outside H&E slides and unstained specimens for PDPN staining will be requested. [name] and [name] will evaluate tumor pathology, cell morphology, and PDPN expression in these patient samples. [name] will evaluate PDPN expression and MASL sensitivity from primary cultures of these cells. Study clinicians will evaluate oral cavity and health of their respective patients before and after MASL treatment. [name], [name], [name], [name], [name] or [name] will administer MASL dosage, evaluate any effects on oral structure and epithelium, and perform clinically indicated resection or biopsy to obtain specimen after treatment. [name], [name], [name], [name], [name] or [name] along with [name] and [name] will measure overall health before and after administration, and evaluate potential allergic reaction to MASL and respond to any unlikely scenarios. [name], [name] and [name] will evaluate pathology, cell morphology, and PDPN expression in these samples. We will determine if MASL treatment can decrease PDPN expression and normalize cell morphology in oral cancers and precancerous lesions.

Thus, primary, secondary, and tertiary objectives are as follows:

- a. Primary Objective: To evaluate and compare the morphology and podoplanin (PDPN) expression of cells included in the oral lesion initial biopsy to normal oral squamous epithelial cells (OSCCs).
- b. Secondary Objective: To evaluate and compare the PDPN expression of cells included in the resected oral lesion to normal oral squamous epithelial cells.
- c. Tertiary Objective: To evaluate and compare the morphology of cells included in the resected oral lesion to normal oral squamous epithelial cells.

### 1.2 Hypotheses

We hypothesize that the majority of oral cancers express PDPN, and that MASL inhibits the growth, migration, and transformed morphology of these cells. Our hypothesis predicts that more PDPN will be expressed in aggressive oral cancer cells (OSCCs) than normal oral epithelium (OSCs), and that MASL will inhibit the growth and migration of these OSCCs in a manner that correlates with PDPN expression *in vitro*, as well as normalize the morphology of these cells *in vivo*.

### 1.3 Primary, Secondary, and Tertiary Endpoints

Endpoints will be determined by cell morphology and PDPN expression examined by IHC. This work will be performed as an integral part of the study. The protocols rely on standard staining protocols to visual cells and PDPN expression with an approved antibody (D2-40). We have experience with this approach as previously described [56].

Our primary endpoint will be measured from patient biopsy material. We will compare the morphology and PDPN expression of cells included in the oral lesion to normal oral squamous epithelial cells. Patients eligible for the study will provide samples with lesion cells that are determined to be OSCC and express more PDPN than normal cells from the same sample specimen. In addition, these OSCC cells will express PDPN levels that are equivalent or greater than PDPN levels expressed by lymphatic endothelial cells (LECs) from the same specimen. Although this may be considered inclusion criteria, it is also an endpoint since these data will confirm that PDPN expression is increased in OSCC cells in our patient population. PDPN expression will be assessed by IHC for this endpoint since it can be used to qualitatively and quantitatively assess PDPN expression and be accomplished along with standard evaluations used for best care practice.

Our secondary endpoint will be measured from patient resection or second biopsy material. We will compare the PDPN expression of cells included in the oral lesion to normal oral squamous epithelial cells. Our secondary endpoint will be met if MASL treated OSCC cells express less PDPN than normal cells from the same sample specimen. In addition, these OSCC cells will express PDPN levels that are lower than PDPN levels expressed by lymphatic endothelial cells (LECs) from the same specimen. Our secondary endpoint will also require that the degree of PDPN expression decrease occurring after MASL administration is greater than any PDPN expression decrease observed after placebo administration. This comparison will be analyzed by t-test to achieve a p value less than 0.05.

Our tertiary endpoint will be measured from the same patient resection or second biopsy material used to measure our secondary endpoint. We will compare the morphology of cells included in the oral lesion to normal oral squamous epithelial cells. Our tertiary endpoint will be met if MASL treated OSCC cells appear less dysplastic than they appeared before treatment. Dysplasia will be graded on a scale of 1 to 5, with 5 being the most dysplastic. Our hypothesis predicts that MASL treated OSCC cells will appear more cuboidal and flatter than they were before treatment.

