[name] and [name] will evaluate PDPN expression and cell morphology by IHC from formaldehyde fixed section of these samples. Surgical specimens will be fixed in 10% formalin in PBS, paraffin embedded, sectioned (4 microns), and processed for hematoxylin/eosin staining and immunohistochemistry D2-40 monoclonal antibody (Dako) to detect PDPN as described [56]. Paraffin-fixed specimens will be prepared by the local oral pathology laboratories at the University Hospital in Newark, NJ as part of the diagnostic histopathology. Routine pathology reports generated during patient care will also be examined to verify the tumor grade and nature of these specimens. Data will be examined by [name] and [name] in a blinded manner with coded labels such that they will not know whether the specimens are from MASL or placebo treated patients.

In addition to IHC analysis, [name] will establish primary cell cultures from these samples. He will evaluate cell morphology, assay PDPN expression by Western blotting, and evaluate the effects of MASL on the growth and migration of these cells by standard growth and motility assays [57]. This work will be performed at the Science Center in Stratford, NJ. Results from these studies will be used to elucidate understand how OSCC cells respond to MASL. However, these cell culture data will not be used as eligibility criteria since these assays may not be accomplished in a time frame consistent with treatment plans. The IHC analysis can be completed within 4 days. Therefore, this testing will not delay any subsequent treatment plans or options.

Patients with OSCC cells that express robust levels of PDPN will be considered for treatment. Robust levels of PDPN will be defined as greater than normal cells and equivalent or greater than PDPN levels expressed by lymphatic endothelial cells (LECs) from the same sample specimen. Patients that meet the eligibility criteria will be enrolled in the treatment phase of this study. Study clinicians ([name], [name], [name], [name], [name] or [name]) will administer MASL or placebo to enrolled subject. Patients will be given a lozenge (troche)with or without MASL added to achieve a final dosage of 100 mg per adult. Clinicians administering the lozenge and [name] are not blinded to the type of the lozenge; however, this information is not available to the pathologist who evaluates tumor pathology, cell morphology, and PDPN expression in the patient samples.

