### **3.3 Sample Size Justification**

We will recruit up to 10 patients for MASL treatment and 10 patients for placebo treatment to attempt a p value of less than 0.05 based on a difference of 40% with respect to Podoplanin expression and MASL sensitivity. Patients will be selected for treatment with MASL versus placebo by 1:1 randomization.

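### The primary endpoint is read on the pre-treatment biopsy and cannot reflect MASL; the randomisation, the 10 + 10 sizing and the only endpoint-linked test serve the comparison ranked secondary

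*Protocol*

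**What the plan says.** **Primary.** Section 1.1 sets the primary objective on morphology and PDPN "expression of cells included in the oral lesion initial biopsy", compared with normal oral squamous cells. Section 1.3 repeats this: "Our primary endpoint will be measured from patient biopsy material", and "We will compare the morphology and PDPN expression of cells included in the oral lesion to normal oral squamous epithelial cells". It adds that eligible patients will have OSCC cells with PDPN above normal cells and at or above lymphatic endothelial cells (LECs) in the same specimen. It then says: "Although this may be considered inclusion criteria, it is also an endpoint since these data will confirm that PDPN expression is increased in OSCC cells".

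**Entry to treatment.** Section 3 admits patients to the treatment phase on robust PDPN: "Robust levels of PDPN will be defined as greater than normal cells and equivalent or greater than PDPN levels expressed by lymphatic endothelial cells". The Schedule of Events lists the same requirement.

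**Secondary.** Section 1.3 uses the resection or second biopsy. It sets three conditions: treated OSCC cells below normal cells, below LECs, and a larger PDPN decrease after MASL than after placebo. The last is tested by t-test at p<0.05.

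**Tertiary.** Dysplasia in MASL-treated cells is compared before and after treatment.

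**Size.** Section 3.3 recruits up to "10 patients for MASL treatment and 10 patients for placebo treatment to attempt a p value of less than 0.05", based on a 40% difference in PDPN expression and MASL sensitivity, with 1:1 randomisation.

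**The concern.** In a randomised placebo-controlled trial, the primary endpoint normally carries the comparison that randomisation protects. Here it is complete before treatment starts, so no effect of MASL, good or bad, can alter it. The between-arm comparison, for which patients are randomised and pathologists are blinded to treatment, sits one rank lower.

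There is a second difficulty. Section 1.3 expects the primary data to confirm that PDPN is raised in OSCC cells in the trial's population. If the data come only from patients admitted because their PDPN was raised, they confirm nothing beyond the entry rule.

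At stake is what the main result means. A report could lead with a finding about baseline biology while the randomised question, on which the sample size rests, is read as supporting evidence.

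**Working it through.** **Step 1: timing.** Section 1.1 places the primary objective on the initial biopsy. The Study Design Flowchart and the Schedule of Events give the order: biopsy, IHC, identification of robust PDPN, lozenge, then resection or second biopsy. The primary measurement therefore precedes dosing. With 1:1 randomisation after it, the expected MASL minus placebo difference in the primary endpoint is 0 for any true drug effect.

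**Step 2: overlap with the entry rule.**

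| | PDPN against normal cells | PDPN against LECs |
|---|---|---|
| Primary endpoint (1.3) | greater | equivalent or greater |
| Entry to treatment (3) | greater | equivalent or greater |

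The two conditions are identical. If 10 + 10 = 20 patients are treated under the rule, the PDPN condition holds in all 20 by selection. This covers the PDPN part only, not morphology.

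**Step 3: the wider denominator.** Section 3 considers up to 50 patients. Section 2 reports raised PDPN in over 30% of precancerous lesions and over 60% of oral cancers. Taking 30% and 60% as round figures, and assuming that raised means roughly the same as the entry threshold, 50 patients would give about 0.30 × 50 = 15 with raised PDPN if all were precancers, and 0.60 × 50 = 30 if all were cancers. In that group the result is not fixed in advance. The protocol does not say which group is meant: 1.3 speaks both of eligible patients and of the patient population.

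**Step 4: which endpoint the design serves.**

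| Design element | Initial-biopsy comparison (primary) | MASL v placebo PDPN change (secondary) |
|---|---|---|
| Hypothesis in 1.2 | yes (PDPN expression) | related (MASL effect on PDPN-expressing cells) |
| 1:1 randomisation (3.3, 3.5.3) | no | yes |
| 10 + 10 sizing (3.3) | no | yes |
| Test tied to an endpoint (1.3) | no | yes |
| Pathologists blinded to arm (3) | no | yes |

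**Step 5: the stated sample size.** Section 3.3 gives no SD, power or sidedness, so 10 per arm can be neither reproduced nor refuted. Assume 40 percentage points, two-sided 0.05 and 80% power. The normal approximation is n per arm = 2(1.96 + 0.842)² × SD²/40²:

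- SD 30: 2 × 7.85 × 900/1600 = 8.8, so 9
- SD 32: 2 × 7.85 × 1024/1600 = 10.05, so 11
- SD 40: 2 × 7.85 × 1600/1600 = 15.7, so 16

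Ten per arm thus corresponds to an SD a little over 30 points.

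**Step 6: what 10 per arm delivers if the between-arm contrast is primary.** Power comes from the noncentral t with 18 df and noncentrality 40/(SD × √(2/10)) = 40/(0.447 × SD):

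| Assumed SD (points) | Noncentrality | Power |
|---|---|---|
| 20 | 4.47 | 98.8% |
| 30 | 2.98 | 80.5% |
| 40 | 2.24 | 56.2% |
| 50 | 1.79 | 39.5% |
| 60 | 1.49 | 29.2% |

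By this calculation, 80% power needs an SD of about 30 points or less. All SDs are assumptions, and 3.3 does not say whether 40% is absolute or relative.

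**The case against.** The ranking has a rationale. Section 1 names PDPN expression before MASL sensitivity, and 1.2 opens with the hypothesis that most oral cancers express PDPN. The plan can be read as a biomarker stage followed by a treatment stage, with the primary endpoint belonging to the first. The protocol also says openly that the endpoint overlaps with entry criteria. Section 5 lists t-tests and ANOVA for study data in general, so the secondary t-test is not the only analysis named. All of this stands, and it shows that the primary endpoint is not arbitrary. It does not connect that endpoint to the randomisation or to the sizing in 3.3, and the two-stage reading is never stated with its own population.

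A reader might go further and infer that the primary endpoint is certain to be met, in 20 of 20 patients, whatever MASL does. The documents do not support that. Section 1.3 gives explicit success rules for the secondary and tertiary endpoints but none for the primary; morphology is part of it; and the denominator may be the wider biopsied group. Only the PDPN condition in treated patients is fixed by selection.

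A reader might also infer that the trial cannot answer whether MASL lowers PDPN. That too goes beyond the text. The between-arm comparison is prespecified, with its test and with blinded reading, at secondary rank.

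**Conclusion.** The mismatch is real and rests on the protocol's own text. The primary endpoint precedes treatment and contains no arm comparison, so it is uninformative about MASL. Its PDPN condition is circular among treated patients (all of up to 20) and informative only if reported on all biopsied patients (up to 50), a denominator the protocol does not fix. It matches the PDPN-expression hypothesis in 1.2 but not the randomisation, the sample size or the endpoint-linked test.

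The consequence is a wrong ranking and an undefined population, not a missing treatment comparison. These conclusions need no numerical assumption. The power figures do: they assume a 40-point absolute difference, a two-sided 0.05 t-test, all 10 patients per arm evaluable, and SDs that the protocol does not give.

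**What to change.** In 1.1 and 1.3:

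- Make the primary endpoint the MASL versus placebo difference in PDPN change from the initial biopsy to the resection or second biopsy, with the existing t-test at p<0.05.
- Keep the two other parts of the present secondary endpoint (treated OSCC cells below normal cells, and below LECs) as separate secondary descriptions, so that they are neither silently dropped nor made conditions of the primary.
- Relabel the lesion-versus-normal comparison on the initial biopsy as descriptive. Report it on all biopsied patients, including those with outside specimens, and not only on those selected for high PDPN.

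In 3.3, state the assumed SD, the sidedness, whether 40% is absolute or relative, and the power that 10 per arm gives for the new primary contrast.

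The cost is amendment wording and one power statement, with no new patients, specimens or assays. The drawback is that the power statement may be unflattering: if the SD is nearer 40 than 30 points, the protocol would have to acknowledge power of about 56% for its primary comparison. That limitation already exists for the same contrast at secondary rank; the change makes it visible.

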### 3. Research Design and Methods

This trial will be conducted in compliance with the protocol, Good Clinical Practice (GCP), and applicable regulatory requirements. Up to 50 patients with visible oral lesions fitting the clinical criteria for cancerous or precancerous lesions undergoing surgery or biopsy (as part of clinical care) at the NJMS or RSDM oral medicine clinic/Rutgers Dental Associates will be targeted for consideration as participants in this study. This includes patients with oral cancer, proliferative verrucous leukoplakia (PVL), conventional oral leukoplakia (OL), and erythroplakia, plus suspect oral papillomas and oral lichen planus. When the identified oral lesion seems appropriate, patients will be asked to sign an informed consent allowing a portion of the biopsy sample or excised tumor to be utilized for research purposes. These specimens will be transferred directly to [name] at Rowan University-SOM for preparation of cell cultures and other research-related testing.

Oral cancers will be sampled surgically by [name], [name], [name], [name] or [name]. Precancerous lesions will be biopsied surgically by [name]. This work will be performed at the NJMS/RSDM/Rutgers Dental Associates and University Hospital in Newark, NJ. Biopsy will be performed by original surgeon as determined by best care practice. These procedures will have been planned as a matter of course for the patient. Therefore, the patients’ participation in this study should not affect their treatment. The operating surgeon will place a sample of the tissue on wet ice. [name] will receive the tissue from the pathology department after they agree that this tissue is not needed for further

analysis. [name] will be waiting in a room as instructed by the surgeon and pathologist and will package the specimens on wet ice and bring them to his lab according to IATA protocols.

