In addition to the process described above, patients already diagnosed with oral cancer/precancer who present to one of the study clinicians for definitive care may also be enrolled in the study if they consent to participation. In these situations, it is routine to request H&E-stained slides from the original surgical pathology department for review as part of the surgical planning for clinical care. For patients who consent, the study clinician or PI would also request 1-3 unstained specimens for D2-40 staining to determine PDPN expression for research purposes. Patients with OSCC cells that express robust levels of PDPN and meet the eligibility criteria will be considered for treatment phase. The remainder of the protocol remains the same.

MASL and placebo lozenges will be prepared by an approved GMP certified facility by chromatography methods established by [name] as described [57]. Lozenges will be stored at the University Hospital Pharmacy and be hand delivered to the administering doctor by study investigators listed on page 1 in a sealed plastic container labeled with the patients name and ID. This work will be performed at the NJMS/RSDM/Rutgers Dental associates and University Hospital in Newark, NJ. [name], [name], [name], [name], [name] or [name] along with [name] and [name] will perform a general physical evaluation of their respective patients before and after MASL or placebo administration. [name] or [name] will

evaluate patient vital signs including temperature, pulse, blood pressure, and overall health after administration. [name] or [name] will also assist with management of any complication should it arise.

In this approach, MASL will find administration through topical exposure to oral lesions in the mouth as the lozenge dissolves. Patients will be asked to dissolve the lozenge in their mouth for at least 5 minutes before being chewed, and refrain from spitting, eating, or drinking for at least 20 minutes after lozenge administration. Subjects will be asked to finish chewing the lozenge within 20 minutes. Systemic exposure through the blood stream may also be accomplished. Data from university studies on cell lines and animal models indicate that MASL can be applied topically or eaten to target PDPN in order to inhibit tumor cell growth and migration. However, pharmacokinetics of this compound have not been established.

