## Schedule of Events

Subject Recruitment	
Identification of patients with premalignant or malignant lesions during the course of clinical care (this includes previously diagnosed oral cancer/precancer patients presenting for surgical resection as part of clinical care)	[name] [name] [name] [name]
informed consent	[name] [name]
Clinical procedures as per best care practice	
Diagnostic tissue biopsy	[name] [name] [name] [name] [name] [name]
Laboratory Procedures	
Diagnostic histopathology, Evaluation of cell morphology & PDPN expression	[name] [name]
Identification of patient samples with robust PDPN expression	
Clinical procedures as per best care practice	
Planning resection or second biopsy	[name] [name] [name] [name] [name] [name]
Treatment Phase	
Evaluation of eligibility criteria for enrolment. Eligible patients: 
 
• Have tissue samples with robust PDPN expression
 
• Have not used topical steroid products within the last 2 weeks
 
• Have Eastern Cooperative Oncology Group performance status of 0 or 1.
 
• Display normal organ function as evidenced by standard laboratory blood tests including liver enzymes and creatine.
 
• Do not present evidence of comorbidities including ongoing or active infection, unstable illness, or medical conditions.
 
• Not pregnant as per standard blood or urine tests according to best care practice
 
• Not breast feeding
 
• Consent to Abstinence or use of adequate contraception (women of childbearing potential and men of reproductive potential)
 
	[name] [name] [name] [name] [name] [name]
MASL administration within 1 week of planned biopsy or resection	[name] [name] [name] [name] [name] [name] [name] [name]
Clinical procedures as per best care practice	
Planned resection or second biopsy	[name] [name] [name] [name] [name] [name]
Laboratory Procedures	
Diagnostic histopathology, Evaluation of cell morphology & PDPN expression	[name] [name]

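### The primary PDPN endpoint repeats the rule that selects patients for treatment, so in selected patients it cannot confirm that PDPN is raised

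*Protocol*

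**What the plan says.** Section 1.1 gives the primary objective as comparing the morphology and PDPN expression of "cells included in the oral lesion initial biopsy to normal oral squamous epithelial cells". It names no PDPN restriction and no analysis population.

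Section 1.3 turns this into the primary endpoint, and the only population it names is a selected one: "Patients eligible for the study will provide samples with lesion cells that are determined to be OSCC and express more PDPN than normal cells". The next sentence adds that lesion PDPN must be at or above that of lymphatic endothelial cells (LECs) in the same specimen. The section then acknowledges the overlap and draws a conclusion from it: "Although this may be considered inclusion criteria, it is also an endpoint since these data will confirm that PDPN expression is increased". The sentence ends by applying this to OSCC cells in the trial's own patient population.

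Section 3 uses the same two conditions as the gate to the treatment phase: "Robust levels of PDPN will be defined as greater than normal cells and equivalent or greater than PDPN levels expressed by lymphatic endothelial cells". The Schedule of Events lists this as an eligibility item for the treatment phase: "Have tissue samples with robust PDPN expression".

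Three other passages bear on the population:
- Section 1.2: "We hypothesize that the majority of oral cancers express PDPN".
- Section 3, on who is considered before any PDPN selection: "Up to 50 patients with visible oral lesions fitting the clinical criteria for cancerous or precancerous lesions". Patients diagnosed elsewhere may also join, using "unstained specimens for D2-40 staining to determine PDPN expression for research purposes".
- Section 3.5.1, the numbered inclusion list, has no PDPN item and admits lesions other than OSCC.

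**The concern.** An endpoint has to be able to come out either way. Here the endpoint conditions and the entry conditions for treatment are the same two inequalities, read on the same specimen. In patients who pass, the direction of the lesion-normal difference is fixed before any analysis, and its average size is inflated because low values have been removed.

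What is at stake is the conclusion attached to the primary endpoint. Data from selected patients cannot show that PDPN is raised in the clinic's OSCC patients. They also cannot address the Section 1.2 hypothesis about the majority of oral cancers, which needs an unselected OSCC denominator.

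The primary endpoint is read on the initial biopsy, before treatment, so it does not compare MASL with placebo. Within Section 1.3 that comparison appears only in the secondary endpoint. Section 3.3 sizes two arms of up to 10 patients without saying which endpoint the size refers to.

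**Working it through.** The plan gives no figure for the primary endpoint, so there is none to reproduce. The core check is logical, and the arithmetic shows its size.

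**1. The two rules side by side**

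| Condition | Primary endpoint (1.3) | Treatment gate (3, Schedule of Events) |
|---|---|---|
| Lesion against normal cells | above | above |
| Lesion against LECs | equal or above | equal or above |
| Material | same specimen | same specimen |

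So P(endpoint conditions met | passed gate) = 1 for any true rate. With the 20 patients of Section 3.3 (10 + 10) the result is 20/20. A nominal two-sided sign test would give 2 × 0.5^20 = 1.9 × 10⁻⁶ whatever the truth.

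**2. Bias in the size of the difference**

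Assumptions: differences are normal across patients, and the gate acts as one cut-off passed by a share p. The mean in passers then exceeds the mean in all biopsied patients by φ(z)/p SD, with z = Φ⁻¹(1 − p). The protocol gives no pass rate for the LEC-level rule, so p is assumed. Section 2 cites raised PDPN in over 30% of precancers, about 50% of T1/T2 cancers, over 60% of oral cancers and about 75% of T3/T4 cancers, without reference to that rule.

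| p | z | φ(z) | Bias (SD) |
|---|---|---|---|
| 0.30 | 0.524 | 0.348 | 1.16 |
| 0.50 | 0.000 | 0.399 | 0.80 |
| 0.60 | −0.253 | 0.386 | 0.64 |
| 0.75 | −0.674 | 0.318 | 0.42 |

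For a given p, a single cut-off gives the largest bias. The real LEC threshold varies between specimens. With an assumed LEC level of mean 0.5 SD and SD 1, independent of the difference, about 30% pass and the bias is about 0.98 to 0.99 SD, against about 1.17 under the single cut-off.

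**3. Worst-case illustration**

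Suppose the true mean difference is zero and only patients with lesion above normal are kept. The mean becomes 0.399/0.5 = +0.80 SD. A one-sample t-test then gives p < 0.05 in 99.8% of simulated samples at n = 10 and in 100% at n = 20. The protocol does not specify this test for the primary endpoint. The run only shows that selected data would look positive when nothing is there.

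**4. What an unselected OSCC denominator could show**

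The number of OSCC patients among those biopsied is not stated, so several sizes are shown. The criterion used here is an exact (Clopper-Pearson) 95% lower limit above 50%.

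| OSCC patients | Smallest count that passes | 95% CI | Chance at true share 60% | Chance at true share 75% |
|---|---|---|---|---|
| 20 | 15 | 50.9% to 91.3% | 12.6% | 61.7% |
| 30 | 21 | 50.6% to 85.3% | 17.6% | 80.3% |
| 40 | 27 | 50.9% to 81.4% | 21.1% | 89.7% |
| 50 (only if all are OSCC) | 33 | 51.2% to 78.8% | 23.7% | 94.5% |

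One patient fewer fails in each row: 14/20, 20/30, 26/40 and 32/50 have lower limits of 45.7%, 47.2%, 48.3% and 49.2%.

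**The case against.** The strongest reply is that the circularity is conditional on where the endpoint is analysed. Objective 1.1(a) is worded without a PDPN restriction, Section 1.3 opens by saying the endpoint is measured on patient biopsy material, and staining is done before the gate. Section 3 also treats the treatment phase as a later step. On that reading all biopsied patients supply the data, and the analysis set could be left to an SAP. This reading is possible, but no sentence adopts it. The one population sentence in the primary-endpoint paragraph names eligible patients, and the paragraph itself accepts the overlap with inclusion. An SAP could name an analysis set, but the protocol's own inference would still stand as written.

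It is also fair that Section 1.3 attaches no test or success threshold to the primary endpoint, that no conclusion about MASL rests on it, and that the overlap is disclosed. Those points limit the damage to the primary endpoint's own claim. They do not make that claim valid.

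The objections to the numbers stand as limits. The SD shifts are upper bounds for a given pass rate. The zero-difference case runs against the protocol's own background figures. The 50% lower-limit criterion is introduced here and is not the protocol's. The logical result in step 1 needs none of them.

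**Conclusion.** The concern holds, with high confidence, and must be fixed because it affects what the primary endpoint can conclude. In patients who pass the PDPN gate, the endpoint conditions are met in 100% by construction, so those data cannot confirm raised PDPN. The mean lesion-normal difference in them is too large by up to 0.42 to 1.16 SD for assumed pass rates of 75% down to 30%, given normal differences and a single cut-off.

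Some information survives selection: how far PDPN exceeds the thresholds can be described, and so can the morphology comparison. On the all-biopsied reading the endpoint would be sound, but the protocol would then leave its population undefined. Its use of the word eligible in Section 1.3 would also conflict with the list in Section 3.5.1.

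**What to change.** In Sections 1.1(a) and 1.3:

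- Define the PDPN endpoint in all consented patients with PDPN staining on the initial biopsy or on an outside specimen, before the PDPN gate. Say whether the limit of 50 includes patients who join with outside specimens.
- Report two proportions, lesion above normal cells and lesion meeting the robust rule, each with an exact 95% CI, separately for OSCC and for precancerous lesions. Report the paired lesion-normal difference in the same population.
- State which of the two rules counts as expressing PDPN in Section 1.2, and assess the majority hypothesis on OSCC patients only.
- Delete the claim of confirmation for gated patients, or label their data as descriptive baseline.

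Two clarifications belong with this. First, state that the randomised comparison is the secondary endpoint and that the Section 3.3 sample size refers to it. Making it primary is optional and would need its own stated SD and power. Second, reconcile the use of eligible in Section 1.3 with Section 3.5.1 and the Schedule of Events.

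The cost is protocol wording and a small extra analysis of staining already planned, with no added tissue or visits. The reported proportion will fall below 100% if any patient fails the gate, and the mean difference will be smaller. With 30 OSCC patients and a true share of 60%, the chance of reaching 21/30 is about 18% (80% at a true share of 75%), so the result may have to be presented as an estimate.
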